1.0 Study Summary

Study Title	Assessment of Sous Vide Water Baths for Acute Rewarming of Frostbitten Extremities
Study Design	Patients with acutely frostbitten hands or feet presenting to the emergency department will be consented to participate in the study. An ANOVA sous vide device will be attached to a water basin and set at 38°C. Two thermometers will continuously monitor water bath temperatures and the readings from the thermometers and sous vide device will be recorded every two minutes. The frostbitten extremity will remain in the circulating warm water bath for 30 minutes, at which time the extremity will be evaluated to see if rewarming is complete (warm to touch, pliable tissue). Tissue that is still frozen will be placed back into the water bath for an additional 30 minutes, at which time they will be reassessed. Medical providers directly involved in the care of the patient will fill out a survey regarding viability of this method and ease of use.
Primary Objective	To assess the ability of sous vide rewarming in maintaining constant water bath temperatures and efficacy in rewarming the acutely frostbitten extremity.
Secondary Objective(s)	To determine the ease of use of sous vide water bath rewarming in the acutely frostbitten extremity.
Research Intervention(s)/ Invest. Agent(s)	ANOVA Precision® Cooker sous vide device
IND/IDE #	NA
Study Population	Patients presenting to the emergency department with acute frostbite requiring rewarming; Providers to conduct rewarming, and complete a survey
Sample Size	1-5 patients locally, with anticipation of multicenter collaboration at 5-10 additional locations with similar enrollment goals.
Study Duration for individual participants	1-2 hours
Study Specific Abbreviations/ Definitions	SVD – sous vide device, SVR – sous vide rewarming

PROTOCOL TITLE: Assessment of Sous Vide Water Baths for Acute Rewarming of Frostbitten Extremities.

2.0 Objectives*

- The purpose of the study will be to describe the use of a sous vide cooking device (SVD) in heating a water bath for the acute treatment of frostbite in the emergency department (ED).
- The aims will be to use this device in the treatment of an estimated 5-20 cases of acute frostbite in the ED, across a multicenter collaboration. The specific aims will be to assess the ability of the device to reach and maintain a target water temperature, and to survey those involved in the management of the patient regarding ease of use of this modality.
- Based on pilot study preliminary data, we hypothesize that the SVD will rapidly heat a small water bath, maintain the target temperature, and be considered easy to use.

3.0 Background*

- Frostbite is a clinical entity in which extremities, digits, and appendages undergo freezing damage due to exposure to environmental cold. Once in a safe environment where the potential for re-freezing is minimal, the current standard of care for acute frostbite is the rapid rewarming of the affected body part, using a circulating warm water bath targeted to 37-39°C. There is no current “best” modality to warm and circulate the water. Depending on resources, this may be difficult and time consuming. In the field, water can be heated over a fire and added to a water bath. If heated water is present, hot tap water can be incrementally added to a water bath to achieve and maintain the targeted temperature. In the ED, some have advocated for placing the frostbitten hand or foot in a sink with running hot water and a thermometer in the sink to detect temperature. These methods are difficult at best, and may be dangerous in that they either do not maintain the water at the targeted temperature, or burn the frostbitten and often insensate extremity. An inexpensive, small, and transportable device that could reliably heat and circulate the water would decrease provider effort and optimize the water bath to the targeted temperature range. In remote locations where electricity is present but not reliably hot water, a portable heating device would drastically improve care.
- This modality is novel, and to our knowledge, has only been used clinically by our research group. In early 2020, a study was published investigating the in vitro use of SVDs in creating

PROTOCOL TITLE: Assessment of Sous Vide Water Baths for Acute Rewarming of Frostbitten Extremities.

circulating warm water baths for the rewarming of frozen pigs' feet. In this study, the SVD maintained the water bath at a constant 40°C for 30 minutes and resulted in the rewarming of the pig foot from frozen to pliable. The sous vide modality was compared against and outperformed manual water exchanges. To test this clinically, we completed a pilot study in 2021 and successfully treated acute frostbite in the ED.

- This study will expand on the first documented use of sous vide rewarming (SVR) in the clinical setting and support proof of concept. Increased patient numbers will demonstrate the efficacy of using this method will provide the foundation for further study of SVR as a rapid, reliable, and portable modality for treating acute frostbite.

4.0 Study Endpoints*

- The primary study endpoint will be the rewarming of frostbitten extremities for 30 minutes at 38°C.
- The secondary study endpoint will be a survey regarding ease of use of this rewarming modality.
- The primary safety endpoint will be patient pain or discomfort that is determined to be unrelated to the discomfort known to be associated with rewarming frostbitten tissue. Two consecutive temperature measurements above 42°C will prompt the cessation of the SVR.

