6.0 Procedures Involved*

- Patients presenting to the ED at Dartmouth-Hitchcock and external study sites with acute frostbite (tissue still frozen) of the hands and/or feet will be identified and approached for recruitment. Patients not entering the study will continue to be treated by ED providers in the traditional fashion.
- Patients recruited for the SVR study will be consented to have their circulating warm water bath(s) heated by the novel SVR method. Providers or nurses caring for the study subjects will be consented to participate and will 1) conduct the SVR procedure, and 2) complete a questionnaire. A researcher will gather SVR equipment and attach two thermometers on the basin: one on the side nearest the SVD, the other on the opposite side. The researcher will verbally walk the provider or nurse carrying out the SVR through the following steps. A 15 L Sterilite® basin will be filled to the marked line (12cm) with water from jugs at room temperature, for each frozen extremity. One extremity can be rewarmed in a single basin, with the possibility for up to four simultaneous SVR basins for a patient with frostbite of all hands and feet. The SVD will be attached to the distal edge of the basin, with one SVD per rewarming basin. The SVD will be turned on and set to maintain the bath at a constant 38°C for 30 minutes duration. The thermometers will be powered on continuously and the researcher will record temperatures simultaneously from each thermometer and the SVD every 2 minutes. At the end of the 30 minute treatment, the extremity will be assessed by the researcher for warmth and pliability. If the extremity still feels cold or frozen, an additional 30 minutes in the water bath will commence, with

PROTOCOL TITLE: Assessment of Sous Vide Water Baths for Acute Rewarming of Frostbitten Extremities.

subsequent reassessment. Rewarming will be considered complete when the affected tissue becomes red or purple, soft, and pliable.

- Patients who do not consent to SVR and elect for traditional water bath management will be asked for their consent to record the similar demographic, water temperature, and time-to rewarm data as in the SVR treatment arm. After re-warming is complete, the provider will be asked to fill out a survey regarding the ease of use and efficacy of the SVR.
- *Describe:*
 - *Procedures performed to lessen the probability or magnitude of risks.*

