 - Dual thermometers will record water bath temperature to assess for the possibility of disequilibrium in water temperature and to detect possible hot spots.
 - The treatment will be terminated if two consecutive thermometer recordings detect water temperatures of 42°C or above.
 - The rewarming process in acute frostbite is inherently painful. Pain increases when water bath temps are above 40°C. No additional discomfort is expected beyond that for frostbite rewarming, at the target temperature of 38°C. The provider can provide analgesia as indicated. The treatment will be terminated if the patient has discomfort that is deemed by the treating provider to be above that expected from rewarming frozen tissue.
 - If treatment is discontinued prior to successful rewarming, standard rewarming will occur.
 - *Explain if any part of this study involves the use of procedures that are inconsistent with the standard of care at Dartmouth-Hitchcock Medical Center.*
 - There are no parts of the study that are inconsistent with the standard of care at DHMC. The novel treatment is to assess a treatment modality that may elevate the standard of care.
 - *All drugs and devices used in the research and the purpose of their use, and their regulatory approval status.*

PROTOCOL TITLE: Assessment of Sous Vide Water Baths for Acute Rewarming of Frostbitten Extremities.

- The ANOVA Precision® Cooker is a purpose-built device to maintain a set temperature circulating water bath. The device is not FDA approved for medical use. There will be no use of a placebo.
- The study treatment takes place entirely in the ED, which allows for comprehensive assessment of protocol compliance. If a subjects opts to discontinue participation at any time during the rewarming, standard techniques for maintaining the water bath will replace the SVD.
- *Describe randomization:*
 - All patients presenting with acutely frostbitten hands or feet will be approached for inclusion in the study. There is no randomization. Any patient not consenting to the use of the SVD but willing to allow data collection will act as a control group.
- *Prior and Concomitant Therapy:*
 - Concomitant therapies, such as intravenous fluids, anti-emetics, forced air warming blanket, and analgesia, as well as other medications deemed necessary by the provider, may be given concomitantly during the treatment period.

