14.0 Withdrawal of Subjects*

- Subjects will be withdrawn without their consent for safety reasons or medical necessity. Criteria as follows: If water bath temperatures are recorded at over 42°C on two consecutive readings during the

PROTOCOL TITLE: Assessment of Sous Vide Water Baths for Acute Rewarming of Frostbitten Extremities.

same treatment phase, if subject is judged by the treating clinician to have pain greater than expected for frostbite rewarming, or if a separate medical issue arises in the subject in which urgent treatment necessitates termination of the research.

- *Describe any procedures for orderly termination.*
 - The SVD will be powered off and the water bath maintained manually by medical staff.
- *Describe procedures that will be followed when subjects withdraw from the research, including partial withdrawal from procedures with continued data collection.*
 - Withdrawal from the research will preclude any further data collection. Data already collected at the time of the withdrawal will be analyzed with other study data but noted that the study terminated prematurely.

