 - While unlikely, it is possible that the SVR would not heat the water and delay time to the current practice of manual water bath management. If this were to occur, delay to therapy would be minimal as the only change in intervention would be the manual addition of warm water to the basin. It is expected that the research treatment will speed up the delivery of effective therapy.
 - Risk will be minimized by assessing the water temperature continuously. The SVR will be ceased and the manual rewarming started if the water bath does not reach the target temperature in 30 minutes, or if the water bath temperature drops below 37°C for more than 5 minutes.
 - If providers are unable to reach an on-call investigator and determine their availability within 20 minutes from the patient expressing interest in the study, standard rewarming will proceed via traditional water exchange practices.
- *If applicable, indicate which procedures may have risks to the subjects that are currently unforeseeable.*
 - Unforeseeable risks different than typical water bath rewarming, if any, would relate to SVD failure. To further minimize this unlikely event the SVD will be physically checked for any signs of wear following each utilization at

PROTOCOL TITLE: Assessment of Sous Vide Water Baths for Acute Rewarming of Frostbitten Extremities.

the time of cleaning. The SVD has been assessed by biomedical engineering at Dartmouth-Hitchcock and deemed low risk.

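### The over-temperature stop has two different thresholds and an undefined two-reading rule; if the readings are the 2-minute recordings, a mandatory stop comes 2 to just under 4 minutes after the bath passes 42°C

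*Combined protocol and SAP*

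**What the plan says.** The protocol states the over-temperature stop three times.

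- Section 4.0, with the safety endpoint: "Two consecutive temperature measurements above 42°C will prompt the cessation of the SVR".
- Section 6.0, among the risk-reduction procedures: "The treatment will be terminated if two consecutive thermometer recordings detect water temperatures of 42°C or above".
- Section 14.0, as a ground for withdrawing a subject: "If water bath temperatures are recorded at over 42°C on two consecutive readings during the", continuing over the page break with "same treatment phase, if subject is judged by the treating clinician".

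The only reading schedule is in section 6.0 (repeated in 17.0): "the researcher will record temperatures simultaneously from each thermometer and the SVD every 2 minutes". The two thermometers sit on opposite sides of the basin and are powered on throughout. Section 15.0 adds: "Risk will be minimized by assessing the water temperature continuously". The limits it then gives are both on the cold side: failure to reach target within 30 minutes, "or if the water bath temperature drops below 37°C for more than 5 minutes".

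On what follows a stop, section 14.0 says: "The SVD will be powered off and the water bath maintained manually by medical staff". Section 6.0 sends any patient stopped before rewarming is complete to standard rewarming, which section 3.0 places at 37-39°C. Section 14.0 also says that withdrawal ends further data collection.

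**The concern.** There are two defects in one safety rule.

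1. **The threshold is inconsistent.** A repeated reading of exactly 42°C stops treatment under section 6.0 but not under sections 4.0 or 14.0.
2. **The confirmation step is undefined.** The two readings could be successive entries on the 2-minute sheet, successive looks at a live display, or the two thermometers at one moment. On the first meaning, the rule waits a full recording interval to confirm something the thermometers in the basin could confirm in seconds.

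Hot-water burns are a listed hazard (section 15.0). The other mandatory stop tied to the bath is pain beyond what rewarming normally causes, yet section 3.0 notes that these limbs often lack sensation, so pain is a weaker warning here than usual. Five to ten further sites are anticipated (section 1.0), and an undefined rule can be applied differently at each.

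**Working it through.** The protocol gives no time-to-stop figure, so there is none to reproduce.

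**Inputs.** Recording interval 2 min (section 6.0). Two consecutive qualifying readings (sections 4.0, 6.0, 14.0). Assumed, not in the documents: the bath crosses 42°C at a time uniform between recordings and stays above; a re-read takes r = 15 to 30 s (0.25 to 0.5 min); independent misreads occur with probability p = 0.1% to 1% per reading.

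**Which meaning of consecutive?** Section 6.0 speaks of recordings, and section 14.0 of values recorded within one treatment phase. Both point to successive entries in time, and the only stated interval is 2 minutes. Against that, section 6.0 also uses the verb *record* for what the thermometers themselves do, and monitoring is continuous. The 2-minute meaning is likely, not certain.

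**Time to mandatory stop, 2-minute meaning.** Let u be the time from crossing to the next recording, from 0 to just under 2 min. The first qualifying reading is at u and the second at u + 2.

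- Range: 2 to just under 4 min. Mean: 1 + 2 = 3 min.
- The choice between *above* and *at or above* moves only the end points.
- An excursion shorter than 2 min cannot span two recordings, so it never forces a stop. Nothing in the documents shows that such excursions occur.

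**Time to mandatory stop with an immediate re-read**, displays checked only at recordings: u + r.

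- Range: 0.25 to under 2.5 min. Mean: 1 + 0.25 = 1.25 to 1 + 0.5 = 1.5 min.

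**If consecutive meant both thermometers at one moment**, the delay would be u, from 0 to just under 2 min. A hot spot seen by one thermometer only would then never force a stop, although detecting hot spots is one stated purpose of having two.

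**False stops.** Chance that either thermometer misreads high at one time point: a = 1 − (1 − p)², which is 0.001999 at p = 0.1% and 0.0199 at p = 1%. A 30-minute basin has 16 recordings (0, 2, …, 30 min).

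| Rule | Formula | p = 0.1% | p = 1% |
|---|---|---|---|
| Current, either thermometer, two successive recordings | about a²[1 + 14(1 − a)] | 0.0060% | 0.58% |
| Re-read, 16 scheduled recordings | 1 − (1 − a²)^16 | 0.0064% | 0.63% |
| Re-read, checks every 30 s (61 checks, assumed) | 1 − (1 − a²)^61 | 0.024% | 2.4% |

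On scheduled readings the re-read costs almost nothing in false stops. With checks every 30 s the rate is about four times the current one. A persistent error, such as a miscalibrated thermometer, breaks the independence assumption and would give higher rates.

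**The case against.** The strongest reply is that the delay rests on one reading of undefined words. The thermometers run continuously, staff are at the bedside, and two consecutive readings could simply be two successive looks. This stands in part: the 2-to-4-minute figure is conditional, and what is certain is that the term is undefined. It does not remove the problem, because the protocol ties no high-side action to the continuous display.

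Second, no harm is shown. This stands. The documents give no injury time at or just above 42°C, the pilot reported no adverse events, biomedical engineering judged the device low risk, and one unanticipated event possibly due to it puts the study on hold. A reader might infer that patients will be exposed to scalding water for up to four minutes. The documents do not support that: the figure is the wait until a stop becomes mandatory, staff may act earlier by judgement or for pain, and nothing indicates how often, or how far, the bath would exceed 42°C.

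Third, a reader might infer that the limb is left in over-limit water after a stop. Section 14.0 does not say to remove it, but section 6.0 already sends the patient to standard rewarming, so stating removal is a clarification.

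Fourth, a faster rule has a cost. Section 14.0 makes the stop a withdrawal that ends data collection, so one hot basin out of up to four could lose the rest of a subject's data. With 1 to 5 patients per site that matters, and the fix has to deal with it.

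**Conclusion.** The point holds as a conditional one. The threshold conflict is certain, though it bites only at a reading of exactly 42°C. The lack of a definition for consecutive readings is also certain. If they are the 2-minute recordings, a sustained excursion forces a stop after 2 to just under 4 minutes (mean 3), against a mean of 1.25 to 1.5 minutes with a re-read taking an assumed 15 to 30 seconds. Both means assume a crossing time uniform between recordings and a bath that stays above the limit. The size of any clinical benefit cannot be estimated from the documents. The change is still worth making, because it settles one safety threshold and shortens confirmation using thermometers already in the basin, while keeping the protection of two readings.

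**What to change.** Put one rule in sections 4.0, 6.0 and 14.0:

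> Any reading of 42°C or above on either basin thermometer prompts an immediate re-read of both within 30 seconds. If either again reads 42°C or above, SVR in that basin stops, the SVD is powered off, and the limb is taken out until the water is promptly corrected to 37-39°C; standard rewarming then continues.

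In section 14.0, state that this stops SVR in that basin only. It does not by itself withdraw the subject, or end data collection for other basins or for follow-up. Record the time and both values of each re-read on the data form, and report every such stop.

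**Cost.** Text changes in three sections, extra fields on the form, and a line in the training e-mail (section 24.0); no new equipment. Some SVR basins will end early, with a short pause out of the water. False stops, under the assumed misread rates, are about 0.006 to 0.63% per 30-minute basin on scheduled readings, rising to about 0.024 to 2.4% if displays are checked every 30 seconds.

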5.0 Study Intervention/Investigational Agent

- 1.1 Description: The intervention will be the use of a sous vide device to heat the water bath to 38°C, rather than the traditional methods of manual water exchanges or placing the frostbitten tissue under running water.
- Drug/Device Handling: The SVD will be stored in a Tupperware container and appropriately labeled. The container will be stored in

PROTOCOL TITLE: Assessment of Sous Vide Water Baths for Acute Rewarming of Frostbitten Extremities.

a locked supply closet and only accessible by providers. This device is not used for other purposes in the ED, however signs on the container will read that this device is to be used only for this study.

- Cleaning the SVD:
 - A sign up chart will be taped to the container housing the SVD. The user will record the date of use, and upon returning the SVD to the container, will check a column indicating that they have sanitized the SVD with Purple SaniWipe cloths and a protocolized dishwasher detergent run.

6.0 Procedures Involved*

- Patients presenting to the ED at Dartmouth-Hitchcock and external study sites with acute frostbite (tissue still frozen) of the hands and/or feet will be identified and approached for recruitment. Patients not entering the study will continue to be treated by ED providers in the traditional fashion.
- Patients recruited for the SVR study will be consented to have their circulating warm water bath(s) heated by the novel SVR method. Providers or nurses caring for the study subjects will be consented to participate and will 1) conduct the SVR procedure, and 2) complete a questionnaire. A researcher will gather SVR equipment and attach two thermometers on the basin: one on the side nearest the SVD, the other on the opposite side. The researcher will verbally walk the provider or nurse carrying out the SVR through the following steps. A 15 L Sterilite® basin will be filled to the marked line (12cm) with water from jugs at room temperature, for each frozen extremity. One extremity can be rewarmed in a single basin, with the possibility for up to four simultaneous SVR basins for a patient with frostbite of all hands and feet. The SVD will be attached to the distal edge of the basin, with one SVD per rewarming basin. The SVD will be turned on and set to maintain the bath at a constant 38°C for 30 minutes duration. The thermometers will be powered on continuously and the researcher will record temperatures simultaneously from each thermometer and the SVD every 2 minutes. At the end of the 30 minute treatment, the extremity will be assessed by the researcher for warmth and pliability. If the extremity still feels cold or frozen, an additional 30 minutes in the water bath will commence, with

PROTOCOL TITLE: Assessment of Sous Vide Water Baths for Acute Rewarming of Frostbitten Extremities.

subsequent reassessment. Rewarming will be considered complete when the affected tissue becomes red or purple, soft, and pliable.

- Patients who do not consent to SVR and elect for traditional water bath management will be asked for their consent to record the similar demographic, water temperature, and time-to rewarm data as in the SVR treatment arm. After re-warming is complete, the provider will be asked to fill out a survey regarding the ease of use and efficacy of the SVR.
- *Describe:*
 - *Procedures performed to lessen the probability or magnitude of risks.*
 - Dual thermometers will record water bath temperature to assess for the possibility of disequilibrium in water temperature and to detect possible hot spots.
 - The treatment will be terminated if two consecutive thermometer recordings detect water temperatures of 42°C or above.
 - The rewarming process in acute frostbite is inherently painful. Pain increases when water bath temps are above 40°C. No additional discomfort is expected beyond that for frostbite rewarming, at the target temperature of 38°C. The provider can provide analgesia as indicated. The treatment will be terminated if the patient has discomfort that is deemed by the treating provider to be above that expected from rewarming frozen tissue.
 - If treatment is discontinued prior to successful rewarming, standard rewarming will occur.
 - *Explain if any part of this study involves the use of procedures that are inconsistent with the standard of care at Dartmouth-Hitchcock Medical Center.*
 - There are no parts of the study that are inconsistent with the standard of care at DHMC. The novel treatment is to assess a treatment modality that may elevate the standard of care.
 - *All drugs and devices used in the research and the purpose of their use, and their regulatory approval status.*

PROTOCOL TITLE: Assessment of Sous Vide Water Baths for Acute Rewarming of Frostbitten Extremities.

- The ANOVA Precision® Cooker is a purpose-built device to maintain a set temperature circulating water bath. The device is not FDA approved for medical use. There will be no use of a placebo.
- The study treatment takes place entirely in the ED, which allows for comprehensive assessment of protocol compliance. If a subjects opts to discontinue participation at any time during the rewarming, standard techniques for maintaining the water bath will replace the SVD.
- *Describe randomization:*
 - All patients presenting with acutely frostbitten hands or feet will be approached for inclusion in the study. There is no randomization. Any patient not consenting to the use of the SVD but willing to allow data collection will act as a control group.
- *Prior and Concomitant Therapy:*
 - Concomitant therapies, such as intravenous fluids, anti-emetics, forced air warming blanket, and analgesia, as well as other medications deemed necessary by the provider, may be given concomitantly during the treatment period.
 - The blood pressure cuff used in the standard emergency department assessment of vital signs will be placed on an extremity that is not currently being rewarmed, whenever possible, to avoid constricting blood flow to the affected tissue.
- *Data Collection:*
 - Prior to rewarming, physical examination of the patient, including the frozen extremity, will be completed and documented in the EPIC/EMR chart by the provider.
 - Two thermometers, placed in the rewarming basin, will continuously monitor the water temperature. The temperature reading on both thermometers as well as the SVD will be recorded on a paper data sheet by a trained provider at 2-minute intervals until the 30 minutes of treatment are complete.

PROTOCOL TITLE: Assessment of Sous Vide Water Baths for Acute Rewarming of Frostbitten Extremities.

- The researcher will repeat an exam, assessing all extremities being treated by SVR, at 30 minutes to determine warmth and pliability of the tissue, confirming thaw. Rewarming will be considered complete if the affected tissue becomes red or purple, soft, and pliable. The same rewarming criteria applies for all extremities.
 - The provider will be asked to fill out a survey on all acute frostbite patients whom consent to the study protocol, as well as those that do not.
 - *The source records that will be used to collect data about subjects. (Attach all surveys, scripts, and data collection forms.) If there are plans for long-term follow-up (once all research related procedures are complete), what data will be collected during this period.*
 - The patient's age and sex will be recorded. The physical examination and pertinent medical information will be reviewed to confirm the location and extent of the frostbite and for contributing conditions.
 - Demographics and relevant medical history will be accessed.
 - Please see attached surveys and data collection forms.
 - Enrolled subjects may be contacted via phone and myDH or local electronic medical record communication at 6 months post-enrollment to assess long term outcomes of their frostbite. Chart review to assess related complications will also occur at this time.
 - *Explain if any part of this study involves genetic analysis of biological specimens. If yes, explain whether the study is based on one the following:*
 - This study does not involve genetic analysis of biological specimens.

Provider Participation:

- *Role/Activities:*

PROTOCOL TITLE: Assessment of Sous Vide Water Baths for Acute Rewarming of Frostbitten Extremities.

- Providers assigned to a patient in the emergency department who is determined to have acute frostbite will be targeted.
- The provider's role will be to identify an acute frostbite patient and ask their patient whether they would be interested in hearing more about and potentially participating in a study assessing a new way to rewarm their frostbitten tissue.
- If the patient agrees, the provider access the study on-call investigator list (posted in the ED provider area) and inform a researcher of the patient and need to discuss the stud and potentially enroll the patient.
- *Recruitment:*
 - Providers assigned to a patient in the emergency department who is determined to have acute frostbite.
- *Eligibility:*
 - Any provider managing a frostbite patient at the training levels of PA, APRN, resident physician, fellow, or attending physician are eligible.
- *Consent Process:*
 - Once the patient has consented to participate, the provider will be consented in an area of the emergency department separate from the patient's room, using the provider consent form.
- *Risks/Benefits:*
 - Risks to providers should be minimal. We do not anticipate providers having any difficulty with voluntary decision-making for this study.
 - Benefits to the provider may include improved work flow due to the decreased labor in maintaining a SVR water bath in comparison to manual water bath management. Additionally, participation will provide a firsthand opportunity to treat acute frostbite with a new modality that has potential for increased use in the future.
- *Data Collection:*
 - After successful completion of the SVR, providers will be asked to take a short, 6-question paper survey regarding ease-of-use of the SVR.

PROTOCOL TITLE: Assessment of Sous Vide Water Baths for Acute Rewarming of Frostbitten Extremities.

- Paper data collection forms will be kept in a locked office until transferred by the PI to a Microsoft excel file on a password-protected DH computer.

